5.3 Schematic diagram

Figure 5.1: Schematic diagram

axSpA=axial spondyloarthritis; CZP=certolizumab pegol; Q2W=every 2 weeks; Q4W=every 4 weeks; SFU=Safety Follow-Up

5.4 Rationale for study design and selection of dose

There are limited data around the optimal duration of treatment in patients with early axSpA and whether it is appropriate to withdraw or reduce treatment at some point in patients who are in remission or low disease activity. The data available to date suggest that anti-TNF therapy withdrawal in patients with active, nonradiographic, and/or early axial spondyloarthritis who are either in remission, or who have an ASAS40 response resulted in a flare (defined as loss of sustained remission, loss of ASAS40 response, or BASDAI >3 at 2 consecutive visits) in the majority (56 to 83%) of patients, resulting in the need to re-establish treatment (Song, 2012; Haibel, 2013; Sieper et al, 2013a). Publications that reported the effects of retreatment after a flare indicated that, in general, patients flaring responded well to retreatment. However, these studies did not provide information on aspects such as whether there is an increased risk of immunogenicity following retreatment. The efficacy of anti-TNF treatment can be maintained

with reduction in dosage in a majority of patients with AS (Cantini et al, 2013; Olivieri et al, 2013). However, there is currently limited evidence related to the impact of dose reduction in patients with early axSpA.

The dose of CZP that will be used in this study is 200mg Q2W with a loading dose of CZP 400mg at Weeks 0, 2, and 4. Although there are 2 approved doses for rheumatologic disease in most regions around the world (loading dose of 400mg CZP at Weeks 0, 2, and 4 followed by CZP 200mg Q2W; 400mg Q4W can be considered), the CZP 200mg Q2W dose is the dose most frequently prescribed around the world. Thus, using the 200mg Q2W dose in this study will provide treating physicians around the world the opportunity to compare the study results with the dose they are most likely to use in their daily practice.

In order to ensure that subjects in the placebo arm or 200mg Q4W arm are not deprived of therapy in case of deterioration of their signs and symptoms, they will be offered escape opportunities to full-dose treatment (CZP 200mg Q2W) during the Double-Blind Period until the end of that period or for at least 12 weeks, whichever is longer.

6 SELECTION AND WITHDRAWAL OF SUBJECTS

6.1 Inclusion criteria

To be eligible to participate in this study, all of the following criteria must be met:

1. An Institutional Review Board (IRB)/Independent Ethics Committee (IEC) approved written Informed Consent Form is signed and dated by the subject or by the parent(s) or legal representative.
2. Subject/legal representative is considered reliable and capable of adhering to the protocol (eg, able to understand and complete diaries), visit schedule, or medication intake according to the judgment of the Investigator.
3. Subject is at least 18 years old and not older than 45 years at the start of Screening Visit.
4. Female subjects must be either postmenopausal for at least 1 year, surgically incapable of childbearing, or effectively practicing an acceptable method of contraception (including oral/parenteral/implantable hormonal contraceptives, intrauterine device, or barrier and spermicide). Abstinence only is not an acceptable method. Subjects must agree to use adequate contraception during the study; and after the last dose of study treatment for at least 10 weeks (or - for participating countries of the European Union - 5 months in accordance with the Summary of Product Characteristics [SmPC]) or longer, if required by local regulations after the last dose of study treatment. Male subjects must agree to ensure that also their female partner(s) use adequate contraception during the study and for at least 10 weeks (or - for participating countries of the European Union - 5 months in accordance with the SmPC) or longer, if required by local regulations after the subject receives their last dose of study treatment.
5. Subjects must have a documented diagnosis of adult-onset axSpA with at least 3 months' symptom duration and meet the ASAS classification criteria for axSpA (according to Appendix 18.1) and symptom duration of less than 5 years prior to the participation of this study.
6. Subjects must have active disease at Screening as defined by

- ASDAS score ≥ 2.1
- BASDAI score ≥ 4
- Spinal pain ≥ 4 on a 0 to 10 NRS (from BASDAI Item 2)
- for mNY-negative subjects only: CRP $>$ upper limit of normal (ULN) and/or current evidence for sacroiliitis on the Screening MRI as defined by a ASAS/Outcome Measures in Rheumatology Clinical Trials (OMERACT) SI-MRI score ≥ 2 and confirmed by central reading

7. Subjects must have had an inadequate response to, have a contraindication to, or have been intolerant to at least 2 NSAIDs. Inadequate response to an NSAID is defined as lack of response to at least 14 days of continuous NSAID therapy at the highest tolerated dose of the administered NSAID.

6.2 Exclusion criteria

Subjects are not permitted to enroll in the study if any of the following criteria is met:

1. Subject has previously participated in this study or subject has previously been assigned to treatment in a study of the medication under investigation in this study.
2. Subject has participated in another study of an investigational medicinal product (IMP) (or a medical device) within the previous 3 months (or five half-lives whichever is greater) or is currently participating in another study of an IMP (or a medical device).
3. Subject has history of chronic alcohol abuse or drug abuse within the last year.
4. Subject has any medical or psychiatric condition that, in the opinion of the Investigator, could jeopardize or would compromise the subject's ability to participate in this study.
5. Subject has a known hypersensitivity to any components of the IMP or comparative drugs as stated in this protocol.

AxSpA disease-related exclusions

6. Subjects must not have fibromyalgia or total spinal ankylosis ("bamboo spine"), or any other inflammatory arthritis, eg, RA, systemic lupus erythematosus, sarcoidosis.
7. Subjects must not have a secondary, noninflammatory condition (eg, osteoarthritis) that in the Investigator's opinion is symptomatic enough to interfere with evaluation of the effect of study medication on the subject's primary diagnosis of axSpA.

Prior medications exclusions

8. Subjects must not have used the following medications in the manner as detailed by the Exclusion Criteria in the following table.

Table 6.1: Concomitant Medications (Prior to Baseline and Study Visits)

Drug class	Dose	Exclusion criteria	Study Visits
Analgesics (including, but not limited to acetaminophen, paracetamol, opiates, or combinations thereof)	Up to maximum approved dose	Any change in stable dose regimen is excluded in the 14 days prior to the Baseline Visit.	Any ad hoc (prn) use of analgesics is not permitted within 24 hours prior to any postscreening visit. Stable dose of analgesics (including narcotics) are permitted throughout the study.
NSAIDs (including cyclooxygenase 2 [COX 2] inhibitors)	Up to maximum approved dose regimen	Any change in stable dose regimen is excluded in the 14 days prior to the Baseline Visit.	Any ad hoc (prn) use of NSAIDs is not permitted within 24 hours prior to any postscreening visit. NSAID dose can be down-titrated at Investigator discretion, if clinically indicated, until Week 28, after which NSAID treatment should remain as stable as possible. NSAID dose should be stable until Week 96 (if subjects have to decrease or stop taking medication due to safety reasons, they may reduce their dose and continue in the study).
Oral corticosteroids	Maximum allowed \leq 10mg daily total prednisone equivalent ^a	Any change in stable dose used for axSpA in the 28 days prior to the Baseline Visit.	A change in the dose is not allowed until Week 96. Oral corticosteroid tapers of less than 14 days used to treat other indication (asthma exacerbation, contact dermatitis, etc) are allowed as long as the maximum daily dose is \leq 20mg. The taper must end at least 1 week before study visit.
Intramuscular (im) corticosteroids	Any dose	Use in the 28 days prior to the Baseline Visit.	Intramuscular corticosteroids must not be used during the study.

Table 6.1: Concomitant Medications (Prior to Baseline and Study Visits)

Drug class	Dose	Exclusion criteria	Study Visits
Intra-articular (ia) corticosteroids	Up to maximum approved dose	Use in the 28 days prior to the Baseline Visit.	SIJ ia corticosteroid injections are not allowed during the study. Peripheral joint injections are permitted.
Intravenous (iv) corticosteroids	Up to maximum approved dose	Use in the 28 days prior to the baseline Visit.	iv doses of corticosteroids may be used during the study for acute illnesses as long as the dose is not given within 1 week prior to Week 12, Week 24, Week 48, or Week 96 and the underlying disease does not present a contraindication to the subject remaining in the study. Indications might include dermatitis, gastroenteritis, asthma exacerbation, and pneumonia.
Hyaluronic acid (ia)	Any dose	Use in the 28 days prior to the Baseline Visit.	After Baseline ia injection of hyaluronic acid may be used in the knee.
SAARDs ^b : SSZ and/or HCQ and/or MTX and/or LFN and /or AZA	Maximum allowed: SSZ \leq 3g daily HCQ \leq 400mg daily MTX \leq 25mg weekly AZA \leq 150mg/day LFN \leq 20mg/day	SAARD use initiated and/or any change in the dose regimen in the 28 days prior to the Baseline Visit. No change is permitted in the route of administration for MTX (im, sc, or oral) in the 28 days prior to the Baseline Visit	SAARDs should be stable until Week 96 (if a subject has to decrease or stop taking medications due to safety reasons, they may reduce their SAARDs and continue in the study).
SAARDs: Cyclosporine, Cyclophosphamide, Mycophenolic acid, Apremilast	Up to maximum approved dose	Use within 28 days prior to the Baseline Visit.	Must not be started during the study.

Table 6.1: Concomitant Medications (Prior to Baseline and Study Visits)

Drug class	Dose	Exclusion criteria	Study Visits
Anti-TNF therapies: IFX ADA ETN GOL CZP	Any dose	For IFX, ADA, and GOL, any use within the 3 months prior to the Baseline Visit. For CZP any exposure history. For ETN, use within the 28 days prior to the Baseline Visit. Only 1 previous biologic is allowed.	Must not be started during the study.
Other rheumatologic therapies: Abatacept tocilizumab ustekinumab tofacitinib Rituximab or other anti-CD20 antibodies	Any dose	Any exposure history.	Must not be started during the study.
Osteoporosis Medications: Risedronate, Alendronate, Ibandronate Denosumab Cathepsin K inhibitor Cinacalcet Calcitonin	Up to maximum approved dose	All stable osteoporosis medications are permitted except for iv bisphosphonates.	Osteoporosis medications with the exception of iv bisphosphonates are allowed without restriction. iv bisphosphonates are not permitted any time within the study.
Intravenous Bisphosphonates: Zoledronic acid Ibandronate Pamidronate	Any dose	Zoledronic acid: any use within the 3 years prior to randomization Ibandronate or pamidronate: any use within the past 2 years.	If iv bisphosphonate treatment is initiated during the study, the subject should be discontinued from study medication.

ADA=adalimumab; AZA=azathioprine; axSpA=axial spondyloarthritis; CD20=Cluster of Differentiation 20;
COX 2=cyclooxygenase 2; CZP=certolizumab pegol; ETN=etanercept; GOL=golimumab;
HCQ=hydroxychloroquine; IFX=infliximab; ia=intra-articular; im=intramuscular; iv=intravenous;
LFN=leflunomide; MTX=methotrexate; NSAID=nonsteroidal anti-inflammatory drug; prn=pro re nata (as needed);
RA=rheumatoid arthritis; SAARD=slow acting antirheumatic drug; SIJ=sacroiliac joint; SSZ=sulfasalazine

^a A table of corticosteroid equivalent doses is provided in Table 18.1 (Appendix 18.2)

^b Throughout the table, we refer to compounds such as sulfasalazine and methotrexate as SAARDs (slow-acting antirheumatic drugs). These medications are also commonly referred to as DMARDs, but since there is no evidence that they are in fact disease-modifying in axSpA (unlike in RA), we have opted for the more appropriate SAARD terminology.

Previous clinical studies and previous biological therapy exclusions

9. Subjects must not have received any nonbiological therapy for axSpA not listed above within or outside a clinical study in the 3 months or within 5 half-lives prior to the Baseline Visit (whichever is longer).
10. Subjects must not have received any experimental biological agents (defined as those agents unlicensed for use in axSpA in Europe or the USA).
11. Subjects must not have received previous treatment with a polyethylene glycolylated (PEGylated) compound that resulted in a severe hypersensitivity reaction or an anaphylactic reaction.
12. Subjects may not have been exposed to more than 1 TNF antagonist prior to the Baseline Visit and may not be a primary failure to TNF antagonist therapy (defined as no response within the first 12 weeks of treatment with the TNF antagonist).

Medical History Exclusions

13. Female subjects who are breastfeeding, pregnant, or plan to become pregnant during the study or within 10 weeks (or – for participating countries of the EU – 5 months in accordance with the SmPC) following the last dose of the investigational product.
14. Subjects with a history of chronic or recurrent infections (more than 3 episodes requiring antibiotics or antivirals during the preceding year), recent serious or life-threatening infection within the 6 months prior to the Baseline Visit (including hospitalization for any infection in the last 6 months or any current sign or symptom that may indicate an infection).
15. Subjects with a history of herpes zoster infection within 6 months prior to the Baseline Visit.
16. Subjects with known TB infection, at high risk of acquiring TB infection, or LTB infection are excluded.
 - a. Known TB infection whether present or past is defined as:
 - Active TB infection or clinical signs and symptoms suggestive of TB (pulmonary or extra pulmonary)
 - History of active TB infection involving any organ system or findings in other organ systems consistent with TB infection
 - Any evidence by radiography or other imaging modalities consistent with previously active TB infection that is not reported in the subject's medical history.
 - b. High risk of acquiring TB infection is defined as:
 - Known exposure to another person with active TB infection within the 3 months prior to Screening
 - Time spent in a healthcare delivery setting or institution where individuals infected with TB are housed and where the risk of transmission of infection is high.

c. Latent TB infection (unless appropriate prophylaxis is initiated prior to study treatment and continued to completion of prophylaxis). Please refer to [Section 12.7.3](#) for further details and instructions.

17. Subjects with current acute or chronic viral hepatitis B or C or with human immunodeficiency virus (HIV) infection.

18. Subjects with current or a history of active infection with histoplasma, coccidioides, paracoccidioides, pneumocystis, nontuberculous mycobacteria, blastomyces, or aspergillus

19. Subjects must not have had a history of an infected joint prosthesis any time.

20. Subjects receiving any live (includes attenuated) vaccination within the 8 weeks prior to Baseline (eg, inactivated influenza and pneumococcal vaccines are allowed but nasal influenza vaccination is not allowed).

21. Subjects who, in the Investigator's opinion, have a high risk of infection (eg, subjects with leg ulcers, indwelling urinary catheter, persistent or recurrent chest infections, and subjects who are permanently bedridden or wheelchair bound).

22. Subjects with a history of a lymphoproliferative disorder including lymphoma or current signs and symptoms suggestive of lymphoproliferative disease.

23. Current malignancy or a history of malignancy, although subjects with less than 3 completely excised basal cell carcinomas or with cervical carcinoma *in situ* successfully surgically treated more than 5 years prior to Screening may be included.

24. Subjects with Class III or IV congestive heart failure as per the New York Heart Association (NYHA) 1964 criteria.

25. Subjects with a history of or suspected demyelinating disease of the central nervous system (eg, multiple sclerosis or optic neuritis).

26. Subjects who have had major surgery (including joint surgery) within 8 weeks prior to Screening or have planned surgery within 6 months of the Screening Visit.

27. Subjects with current or history of severe, progressive, and/or uncontrolled renal, hepatic, hematological, endocrine, pulmonary, cardiac, or neurological disease, as determined by the Investigator.

28. Subjects with significant laboratory abnormalities included but not limited to:

- Liver function tests $>2.0 \times \text{ULN}$
- Estimated Glomerular Filtration Rate (GFR) as measured by Chronic Kidney Disease Epidemiology Collaboration (Levey et al, 2009) $<60 \text{ mL/min}/1.73\text{m}^2$
- White blood cell (WBC) $<3.0 \times 10^9/\text{L}$

29. Subjects with any other condition that, in the Investigator's judgment, would make the subject unsuitable for inclusion in the study.

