3 STUDY OBJECTIVES

The following key definitions are provided as a reference for understanding the study objectives and are used throughout the protocol.

Sustained remission is achieved when a subject has an ASDAS <1.3 at Week 32 or Week 36 (if ASDAS <1.3 at Week 32, it must be <2.1 at Week 36 [or vice versa]) and at Week 48. A subject is eligible for Part B of the study only if sustained remission is achieved in Part A.

A flare occurs when a subject has an ASDAS ≥ 2.1 at 2 consecutive visits or ASDAS >3.5 at any visit during Part B.

Subjects who meet the criteria of flare during Part B and who crossed-over to full-dose treatment (CZP 200mg Q2W) are regarded as escapers.

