Abs=antibodies; ADAb= anti-CZP antibody; AEs=adverse events; AS=ankylosing spondylitis; AsQoL=Ankylosing Spondylitis Quality of Life; axSpA=axial spondyloarthritis; BASDAI=Bath Ankylosing Spondylitis Disease Activity Index; BASFI=Bath Ankylosing Spondylitis Functional Index; BASMI=Bath Ankylosing Spondylitis Metrology Index; CRP=C-reactive protein; CZP=certolizumab pegol; EQ-5D=EuroQoL Health Status Questionnaire; H=home, no site visit; HIV=human immunodeficiency virus; HLA-B27=human leukocyte antigen B27; HN=home nurse visit at subject's home; IBD=Inflammatory bowel disease; incl.=including; inj= injection; IXRS=Interactive Voice or Web Response System; MASES=Maastricht Ankylosis Spondylitis Enthesitis Score; MRI=magnetic resonance imaging; PE=physical exam; sc=subcutaneously; SF-36=Short-Form 36-item Health Survey; SFU=Safety Follow-Up; SI=sacroiliac; subj=subject; TB=tuberculosis; W=Week; WD=Withdrawal; WHO=World Health Organization

^a Assessments conducted 3 to 5 days prior to Week 48 will serve as the qualification assessments for subjects determined to be eligible for randomization into Part B at Week 48.

^b SFU: 10 weeks after last dose of study medication.

^c Informed consent: Prior to any study activities, subjects will be asked to read and sign the informed consent form for the conduct of the study. A separate informed consent form will be obtained from subjects consenting also to the use of their blood samples for possible genetic, genomic, and proteomic analysis.

^d Pulse rate, systolic and diastolic blood pressures, temperature, and respiration rate are to be measured at Screening and Baseline, thereafter pulse rate, systolic and diastolic blood pressures and temperature are to be measured. If a subject experiences an AE, respiration rate will be measured in addition.

^e Testing to rule out hepatitis B surface antigen, antibodies to hepatitis C, antibodies to HIV and HLA-B27 at Screening only.

^f To be assessed as indicated and from Week 52 onwards every 4 weeks only.

^g Pregnancy testing for women of childbearing potential will be serum testing at the Screening Visit and SFU and urine testing at Baseline and Week 96/WD Visit.

^h Includes evaluation of signs and symptoms of active TB and risk factors for exposure to TB. Weight is to be measured at Screening, Baseline, Week 48, and at Week 96/WD. Height will be measured at the Baseline Visit only.

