7.8.1 Permitted concomitant treatments (medications and therapies)

The following concomitant medications/treatments are permitted during the study, from Baseline onward, with restrictions as specified:

- NSAIDs/cyclooxygenase 2 (COX-2) inhibitors: doses should be stable throughout the study and ad hoc as needed (prn) inhibitors should not be used 24 hours prior to any post-Screening study visit. No change in dose or dose regimen is allowed during the study except for reasons of safety, where the NSAIDs/COX-2 inhibitors dose may be decreased or discontinued. NSAID dose may be down-titrated at Investigator discretion. The reduction in NSAID dose if clinically indicated is permitted at the discretion of the Investigator until Week 28, however after that timepoint the NSAID treatment should remain stable as much as possible.
- Stable doses of analgesics (including, but not limited to acetaminophen, paracetamol, NSAIDs, opiates or combinations) will be permitted except that ad hoc (prn) usage is prohibited within the 14 days prior to Baseline or 24 hours prior to any post-Screening assessments.
- Corticosteroids (see [Section 7.8.2](#) for prohibited corticosteroids):
 - Oral chronic stable doses are allowed as long as the maximum daily total prednisone equivalent dose is ≤ 10 mg. Oral corticosteroid tapers of less than 14 days used to treat other indications (asthma exacerbation, contact dermatitis, etc.) are allowed as long the maximum daily dose is ≤ 20 mg. The taper must end 1 week before a study visit.
 - Intra-articular (ia): ia administrations of corticosteroids are permissible in peripheral joints; however, after an ia injection the joint will no longer be evaluated for data regarding swollen and tender joints.
 - Intravenous (iv): iv administration of corticosteroid will be permitted for the purposes of stress dosing for a surgical procedure under general or spinal anesthesia. Furthermore, iv administration of corticosteroids may be used during the study for acute illnesses as long as the dose is not given within 1 week prior to Week 12, Week 24, Week 48, or Week 96, and the underlying disease does not present a contraindication to the subject remaining in the study. Indications might include dermatitis, gastroenteritis, asthma exacerbation, and pneumonia.

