14.2 General statistical considerations

All efficacy analyses for Part B will be performed using the RS. The FAS and PPS will be used for a sensitivity analysis on the primary endpoint only. Efficacy summaries for variables collected in Part A will be based on the OLS.

Summaries at the Week 48 timepoint for laboratory data and data collected via electronic device (Site Tablet) will be based on the assessments conducted 3 to 5 days prior to the Week 48 clinic visit.

The statistical analysis of the primary efficacy variable will account for the testing of multiple doses by using a fixed sequence testing procedure. The proportion of subjects who do not experience a flare (where flare is defined as ASDAS ≥ 2.1 on 2 consecutive visits or ASDAS > 3.5 at any visit) will be compared between each CZP dose and placebo. The predefined order of

hypotheses testing, each at a 2-sided 0.05 significance level for the comparison between the given CZP dose and placebo, will be performed in the sequence shown below:

1. CZP 200mg Q2W vs placebo
2. CZP 200mg Q4W vs placebo

The second test will be performed irrespective of whether the first test is significant at the 0.05 level or not. However, the second test will be interpreted as statistically significant only if the first test is significant at the 0.05 level as well.

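### The iv corticosteroid restriction is not aligned with the three ASDAS assessments that decide entry to Part B: none has a full steroid-free week before it

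*Protocol*

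**What the plan says.** On iv corticosteroids, Protocol 7.8.1 states that "iv administration of corticosteroids may be used during the study for acute illnesses", and both 7.8.1 and Table 6.1 (Section 6.2) attach the same condition: "as long as the dose is not given within 1 week prior to Week 12, Week 24, Week 48, or Week 96". Section 7.8.2 treats any corticosteroid use outside 7.8.1 as prohibited and requires withdrawal before a prohibited medication is started.

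On entry to Part B, Section 3 says: "Sustained remission is achieved when a subject has an ASDAS <1.3 at Week 32 or Week 36". The other of those two scores must be below 2.1, and the score at Week 48 must again be below 1.3.

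On the timing of the Week 48 score, footnote a of Table 5.1 says: "Assessments conducted 3 to 5 days prior to Week 48 will serve as the qualification assessments". Section 14.2 agrees: Week 48 summaries of laboratory and tablet data "will be based on the assessments conducted 3 to 5 days prior to the Week 48 clinic visit". Section 8.3.2 places CRP, BASDAI and PtGADA, which together supply every ASDAS component, at that earlier assessment.

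The oral rule in Table 6.1 has no list of weeks: "The taper must end at least 1 week before study visit".

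**The concern.** A steroid-free week before an assessment keeps a short-lived drug effect out of CRP and the patient-reported items. The iv rule gives that week at four named visits. Two of them, Weeks 12 and 24, decide neither remission nor flare. Two of the three assessments that do decide randomization, Weeks 32 and 36, are not named. The third is protected by counting back from the Week 48 visit, although the blood and questionnaires come from 3 to 5 days earlier.

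What is at stake is the meaning of sustained remission. A site can follow the rule exactly and still give an iv dose a few days before a score that decides whether a subject is randomized or discontinued.

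**Working it through.** The protocol states no coverage figure, so there is none to reproduce. The check lines up the dates.

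**Inputs.** Restricted periods in Part A: the 7 days before Weeks 12, 24 and 48 (Table 6.1, 7.8.1). Deciding assessments: Week 32, Week 36 (Section 3), and Week 48 minus *k* days with *k* = 3 to 5 (Table 5.1, footnote a). Length of Part A: 48 × 7 = 336 days.

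**Coverage.** Of the 7 days before each assessment, count those inside a restricted period. For the Week 48 qualifying assessment this is 7 − *k*.

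| Deciding assessment | Days covered, of 7 |
|---|---|
| Week 32 | 0 |
| Week 36 | 0 |
| 3 days before Week 48 | 7 − 3 = 4 |
| 4 days before Week 48 | 7 − 4 = 3 |
| 5 days before Week 48 | 7 − 5 = 2 |

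Fully covered: 0 of 3. A compliant dose 8 days before Week 48 falls 8 − 5 = 3 to 8 − 3 = 5 days before the deciding assessment. Section 7.8.1 also permits iv stress dosing for surgery with no timing limit; that is left out of this count.

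**Could a dose matter to a borderline score?** ASDAS contains 0.579 × ln(CRP + 1) (Section 9.1.7). The protocol gives no steroid effect on CRP, so the following falls are assumptions:
- (CRP + 1) down by a quarter: 0.579 × ln(4/3) = 0.17.
- (CRP + 1) halved: 0.579 × ln 2 = 0.40.

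A subject whose score would otherwise be 1.5 would read 1.5 − 0.17 = 1.33 in the first case and fail, and 1.5 − 0.40 = 1.10 in the second and pass. The acute illness itself could raise CRP and push the score the other way.

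**Can one dose qualify a subject?** A dose before Week 32 or 36 affects one of the earlier pair. The subject must still score below 1.3 at the Week 48 assessment, roughly 12 to 16 weeks later. A dose shortly before the Week 48 assessment affects the last condition, but one of the two earlier scores must already be below 1.3 and the other below 2.1.

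**Cost of closing the gap.** Restricted days now: 3 × 7 = 21. With Weeks 32 and 36 added, and the Week 48 period running from 7 days before the qualifying assessment to the visit: 4 × 7 + (7 + 3 to 5) = 28 + 10 to 12 = 38 to 40 of 336, an increase of 17 to 19 days.

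**The case against.** **Purpose.** The protocol never says that the window exists to protect the entry assessments; Weeks 48 and 96 are also the secondary-endpoint timepoints. That is fair, and the purpose is inferred. But a rule that protects Week 48 data for any purpose should count from the day those data are collected.

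**Reading of Week 48.** Because Section 14.2 equates Week 48 data with the earlier assessment, a site might count the week back from there. That would cover 1 of 3, but Section 14.2 governs summaries, not dosing, and Weeks 32 and 36 stay open.

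**Robustness of the criterion.** Remission needs three scores, so one transient dose before Week 32 or 36 cannot carry a subject through. This stands and limits the size of the problem.

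**The wider reading.** A reader might infer that the primary comparison is threatened, since Part B has 13 ASDAS assessments (Weeks 50, 52, then every 4 weeks to 96) and the iv window covers only Week 96. The documents do not support that:
- The endpoint is whether any flare occurs, defined by ASDAS of at least 2.1 "at 2 consecutive visits or ASDAS >3.5 at any visit during Part B". If a steroid breaks a pair, a persisting flare is normally recorded later.
- Of the 12 visits that can confirm a raised score (Weeks 52 to 96), 10 leave at least one later pair. Weeks 92 and 96 leave none, but Week 96 is covered, so for acute-illness iv doses only Week 92 is unrecoverable.
- Iv doses are allowed for conditions such as pneumonia or gastroenteritis, so the direction of any effect on ASDAS is unknown.

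A reader might also point to joint injections: "SIJ ia corticosteroid injections are not allowed during the study. Peripheral joint injections are permitted", with no on-study timing rule. That is an explicit permission with its own data rule (the injected joint leaves the joint counts). Restricting it further is a design preference.

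**Conclusion.** The mismatch is real and sits in operative text that the protocol itself fixes: 0 of 3 entry-deciding assessments has a full week free of iv steroids, with the Week 48 assessment covered for 2 to 4 of 7 days. The consequence is that a borderline subject could be classified as in or out of sustained remission on a steroid-affected score. This bears on who is randomized. It does not bias the comparison between arms, because the doses in question precede randomization, and no loss of power or type I error control follows from it.

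The effect is probably small. That judgement rests on iv treatment for acute illness being uncommon at these particular times, which the protocol does not quantify, and on the need for three qualifying scores. This is a cheap improvement, not a flaw in the primary analysis.

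**What to change.** In Table 6.1 and in 7.8.1, change the list in the iv rule to: *Week 12, Week 24, Week 32, Week 36, the assessment 3 to 5 days prior to Week 48 (through the Week 48 visit), or Week 96*.

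The cost is the extra 17 to 19 restricted days in Part A. A subject who needs an iv dose on one of those days would fall under the withdrawal rule in 7.8.2, as already happens in the week before Weeks 12, 24 and 48.

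No change is proposed to the Part B dosing rules, the flare definition or the primary analysis. Extending the iv window to every Part B visit would force withdrawals that Section 14.3.1 counts as flares. If the sponsor wants a sensitivity analysis for steroid use in Part B, it belongs in the SAP and should treat post-steroid ASDAS values symmetrically, above and below 2.1, so that it can remove flares as well as add them.
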